Human Platelet Extract
(HPETM) is an effective topical cosmetic product for anti-aging and facial rejuvenation.

NCT05457491

4/19/2022

General Study Information

Effective: 9/20/2017

Principal Investigator: [name]., Ph.D.

Study Title: Novel Antiaging Regenerative Skin Care Regimen Containing Human Platelet Extract (HPE)

Protocol version number and date: Version 06 – April 19, 2022

Research Question and Aims

Hypothesis: Human Platelet Extract (HPETM) is an effective topical cosmetic product for anti-aging and facial rejuvenation.

Aims, purpose, or objectives:

The objective of this cosmetic study is to evaluate the role of HPE on aging skin appearance.

To assess the effect of HPE on fine lines/wrinkles, skin tone/texture, erythema, and pigmentation.

To compare the effect of HPE to market-competitor topical antioxidant (SkinceuticalsTM CE Ferulic).

Background (Include relevant experience, gaps in current knowledge, preliminary data, etc.):

Skin aging is caused by free radical destruction of proteins, lipids, deoxyribonucleic acid (DNA), ribonucleic acid (RNA), organelles, and other vital structures. Under normal conditions, free radical damage is repaired by antioxidants, but these unfortunately decline with age, increasing the likelihood of continuous damage. Oxidative stress occurs when there is a loss of balance between free radical damage and cellular antioxidant self-repair [1]. This balance favors oxidation as small, nontoxic amounts of reactive oxidative species are required for cellular communication, immune system function, and control of the cell life cycle, which leads to beneficial cellular adaptation and balance. The skin also receives damage from free radicals generated by external factors, such as air pollutants, smoking, and changes in humidity and temperature [2]. These extrinsic causes of skin aging become more pronounced on sun-exposed areas such as the face and dorsal hands.

The visibility of the skin represents a unique organ system that facilitates inspection following application of topical formulations. The scientific literature is replete with evidence supporting the beneficial effects of many minerals, vitamins, antioxidants, anti-inflammatories, and growth factors in terms of skin hydration and firmness. Here, we describe and evaluate HPE formulation designed to improve skin appearance.

Non-FDA Approved Drug/Products

This study is testing non-FDA approved cosmetic products:

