Lauded for its superior antioxidant benefits, this highly potent form of pure vitamin C helps neutralize free radicals and protect against oxidative stress while providing visible anti-aging henefits

1% alpha tocopherol

This pure form of vitamin E neutralizes free radicals and replenishes skin lipids. It has been proven to act synergistically with vitamin C.

0.5% ferulic acid

A plant-based antioxidant, ferulic acid neutralizes free radicals and enhances the antioxidant benefits and stability of vitamins C and E.

Learn more about L-ascorbic acid

Learn More About Ferulic Acid

See All Ingredients

aqua / water / eau, ethoxydiglycol, ascorbic acid, glycerin, propylene glycol, laureth-23, phenoxyethanol, tocopherol, triethanolamine, ferulic acid, panthenol, sodium hyaluronate

Study Design and Methods

Methods: Describe in lay terms, completely detailing the research activities that will be conducted by Mayo Clinic staff under this protocol.

80 participants over the age of 40 with moderate photoaging (dyschromic facial skin with fine lines and wrinkles) will be recruited from Mayo Clinic Center for Aesthetic Medicine and Surgery (CAMS) to participate in this study. After signing written informed consent, eligible subjects will be instructed to apply topical HPE to entire face and decolletage twice daily, in the morning and at bedtime. In addition, subjects will be instructed to apply topical HPE to the right dorsal hand and market-competitor group (SkinceuticalsTM C.E. Ferulic) to left dorsal hand. Select subjects (n=20) will also apply topical HPE to the right upper inner arm for skin biopsies at week 12. A baseline skin biopsy will be obtained from untreated skin on the left upper inner arm from the same subjects. Subject renumeration will be provided for skin biopsies.

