 The study involves data that exist at the time of IRB submission and data that will be generated after IRB submission. Include this activity in the Methods section. Examples The study plans to conduct a retrospective chart review and ask subjects to complete a questionnaire. The study plans to include subjects previously diagnosed with a specific disease and add newly diagnosed subjects in the future. 					
The study will use data that have been collected under another IRB protocol. Include in the Methods section and enter the IRB number from which the research material will be obtained. When appropriate, note when subjects have provided consent for future use of their data and/or specimens as described in this protocol.					
Enter one IRB number per line, add more lines as needed					
Data Specimens Data & Specimens					
☐ Data ☐ Specimens ☐ Data & Specimens					
☐ Data ☐ Specimens ☐ Data & Specimens					
Data Analysis					

Power analyses may not be appropriate if this is a feasibility or pilot study, but end-point analysis plans are always appropriate even if only exploratory. Provide all information requested below, or provide justification if not including all of the information.

Data Analysis Plan:

All continuous data will be analyzed using independent 2-group t tests and reported as means \pm standard deviations. Categorical data will be compared between the 2 groups using chi-square tests and reported as counts and percentages. Nonparametric equivalents Wilcoxon rank-sum and Fisher exact tests will be used as needed for nonnormal distributions and low variable numbers, respectively. Treatment effects on outcomes will be compared between baseline versus HPE and HPE versus market competitor group with a significance level of p < 0.05.

Endpoints

Primary:

Evaluation of the tolerability of the study product.

- a. Nature, incidence, and severity of adverse events (AEs)
 - 1) Defined as any untoward or undesirable medical occurrence in the form of signs, symptoms, abnormal findings, or diseases that emerge or worsen relative to baseline (i.e., if present upon study entry) during the study regardless of causal relationship.
 - 2) Assessment
 - i. Incidence and severity of AEs (mild, moderate, severe)
 - ii. Relationship of AEs to study product (probable, possible, unlikely, unrelated)
 - 1. If possibly or probably related to the study product, determine whether related to the product itself or procedures pertaining to delivery of the study product.

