Additionally, Canfield shall take all appropriate technical and organizational measures which are necessary to prevent the unauthorized or unlawful processing of, the unauthorized or unlawful disclosure of and/or the accidental loss or destruction of, or damage to, such data, including without limitation, implementation and enforcement of administrative, technical and physical security policies and procedures. Incident Reporting. Canfield shall promptly notify Sponsor in the event of a security breach or incident involving any data which Canfield is processing on behalf of Sponsor.

Study procedures

The skin biopsies, skin swabs and long-term follow-up visits will be obtained separately from 80 subjects.

- n=80 subjects
- Entire face and decolletage HPE (n=80)
- HPE (n=80) to be applied on the right dorsal hand
- Skinceuticals CE Ferulic (n=80) to be applied on the left dorsal hand
- Skin biopsy (baseline): Left upper inner arm untreated (n=30)
- Skin biopsy (week 12): Right upper inner arm HPE treated (n=30, same subjects as above)
- Microbiome analysis (baseline): Left and right malar cheek untreated (n=80 with both skin swab and tape-stripping method)
- Microbiome analysis (week 12): Left and right malar cheek HPE treated (n=80 with both skin swab and tape-stripping method)

N=30 - Skin biopsy: Two total skin biopsies will be performed per subject (n=30 subjects). In this study, we will remove a small piece of skin from untreated skin on the left upper inner arm (baseline) and HPE treated area on the right upper inner arm (week 12). This is called a skin biopsy.

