- Topical treatment jars will be weighed to ensure correct application amount.
- Subject treatment log will be reviewed.

Specific assessment (cosmetic evaluation questionnaires)

- Global Aesthetic Improvement Scale
- Cosmetic Improvement Scale

Treatment assessment

Continuation of topical HPE twice daily on the face and decolletage only as indicated for 20 subjects.

- Study staff will re-demonstrate treatment application.
- Each subject will receive their second cosmetic kit, which will include gentle cleanser, unscented bar soap, HPETM product, SkinceuticalsTM CE Ferulic serum, sunscreen and moisturizer.
- For questions, subjects will be provided contact email: [contact]

Visit 3 and 4: Long-term follow-up at 26- and 52-weeks. Cohort 2 (n= up to 80)

VISIA-CR imaging

- Photography
- Topical treatment jars will be weighed to ensure correct application amount.
- Subject treatment log will be reviewed.

Specific assessment (cosmetic evaluation questionnaires)

- Global Aesthetic Improvement Scale
- Cosmetic Improvement Scale

Figure 1: Study Summary

Face and decolletage (n=80)

Right dorsal hand (n=80)

Right inner arm (n=30)

HPE

. . . .

- Week 0
- · VISIA-CR imaging
- Photography
- · Skin microbiome

Week 6

- · VISIA-CR imaging
- Photography
- Questionnaires

Week 12

- · VISIA-CR imaging
- Photography
- Questionnaires
- Skin microbiome

Week 26 and Week 52

- VISIA-CR imaging
- Photography
- Questionnaires

HPE

Left dorsal hand (n=80)

Skinceuticals C.E. Ferulic

Week 0, 6 and 12

- VISIA-CR imaging
- · Photography
- Questionnaires

HPE – week 12 biopsy

Left inner arm (n=30)

Untreated – week 0 biopsy

Week 0

- Skin biopsy (untreated) Week 12
- Skin biopsy (HPE)

Table 1: Summary of Monitoring and Follow-Up Assessments

Assessment	Screening / Baseline Visit (Visit 0)	6 Weeks (Visit 1) (±4 Days)	12 Weeks (Visit 2) (±7 Days)	26 Weeks* (6 months) (Visit 3) (±14 Days)	52 Weeks* (12 months) (Visit 4) (±30 Days)
Informed Consent and HIPAA Authorization	X				_
Questionnaires and Assessments	All Encounters				
Skin biopsy*	X		X	_	_
Microbiome analysis (skin swab and tape-stripping)	X	_	X	_	_
VISIA-CR imaging	X	X	X	X	X
Photography	X	X	X	X	X
AE Evaluation	All Encounters				
Medical History	X	_	_	_	_

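### HPE is always on the right hand and the competitor always on the left, so the only HPE-versus-competitor comparison cannot be separated from side-dependent change over 12 weeks.

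*Combined protocol and SAP*

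**What the plan says.** The Aims include "To compare the effect of HPE to market-competitor topical antioxidant", and the Data Analysis Plan lists HPE versus competitor among its tests. The hand assignment is the same in three places. Methods tells subjects to "apply topical HPE to the right dorsal hand and market-competitor group (SkinceuticalsTM C.E. Ferulic) to left dorsal hand". Study procedures gives "HPE (n=80) to be applied on the right dorsal hand" and "Skinceuticals CE Ferulic (n=80) to be applied on the left dorsal hand". Figure 1 repeats the layout with 80 right and 80 left hands.

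The face, decolletage and treated inner arm receive HPE only. The section on the 2X concentration substudy names face and neck imaging and mentions neither hands nor a competitor. Bilateral hand images are part of the primary photoaging endpoint, which is a change from baseline. For the analysis the plan states: "All continuous data will be analyzed using independent 2-group t tests".

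The plan does not randomise or alternate side, does not name handedness among the baseline data, and has no side term.

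**The concern.** Each subject serves as her or his own control, which is a sound idea, but every subject has the same layout. Knowing the side is knowing the product. Anything that makes the right hand change differently from the left during the 12 weeks, such as hand use, incidental sun or the way product is applied, enters the estimate exactly as a product effect would. It could create a product difference or hide a real one.

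The hands are the only place where the comparative aim can be met, so that aim has no second source of evidence.

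**Working it through.** The plan gives no power calculation, effect size, SD or between-hand correlation, so there is no stated figure to reproduce.

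**1. Identification (no assumed numbers).** Let D be the HPE-hand change minus the competitor-hand change within a subject, τ the product effect, and δ the right-minus-left difference in change due to side.
- Fixed sides: E(D) = τ + δ for all 80 subjects. With columns for intercept, product and side, the design matrix has rank 2 of 3.
- Side randomised: E(D) = τ + δ when HPE is on the right and τ − δ when it is on the left. The rank is 3 of 3, and the average of the two group means estimates τ.

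**2. Could another part of the plan supply the missing contrast?** Figure 1 lists the left hand at weeks 0, 6 and 12. Visit 2 then says "Continuation of topical HPE twice daily on the face and decolletage only", with a reference to 20 subjects. The week-12 kit lists the competitor serum again, but nothing assigns it to the other hand. No reversed-side data arise.

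**3. Sensitivity to a side shift.** From the plan: n = 80 and alpha 0.05. Assumed: a two-sided test, τ = 0, δ in SDs of the within-person difference, and between-hand correlation ρ.

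The paired test uses the non-central t with 79 df and non-centrality δ√80. For the planned independent test, correlated pairs were simulated with unit SD per hand and a shift of δ√(2(1−ρ)).

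| Side shift δ (SD) | Paired test (not planned) | Planned test, ρ = 0.3 | Planned test, ρ = 0.5 | Planned test, ρ = 0.7 |
|---|---|---|---|---|
| 0 | 5% | 2.0% | 0.6% | 0.05% |
| 0.1 | 14% | 7.5% | 3.2% | 0.4% |
| 0.2 | 42% | 29% | 16% | 4.0% |
| 0.3 | 76% | 63% | 46% | 19% |

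The planned test starts well below 5% because it ignores the pairing. That does not reduce the bias in the estimate, which is δ in every cell.

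**4. Side shift that alone puts the expected result at p = 0.05.**
- Paired: t(0.975, 79)/√80 = 1.990/8.944 = 0.22 SD.
- Planned: t(0.975, 158)·√(2/80)/√(2(1−ρ)) = 0.312/√(2(1−ρ)), which is 0.26, 0.31 and 0.40 SD at ρ = 0.3, 0.5 and 0.7.

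For scale, 80 pairs give 80% power for a product effect of 0.32 SD.

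**5. Side randomised 40/40 with a side term.** The variance of the estimate is (σ²/4)(1/nR + 1/nL), where nR and nL count subjects with HPE on the right and on the left. The effective n is therefore 4/(1/nR + 1/nL) = 4/(1/40 + 1/40) = 80. In simulation with side shifts of 0.1, 0.2 and 0.3, the mean bias was 0.00 and rejection was 4.9%, 5.0% and 5.1%. The detectable difference stays at 0.32 SD on 78 df.

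**The case against.** The plan already covers part of the risk. Exclusion 5 removes subjects with asymmetric photodamage or marked surface differences between the hands. Change from baseline cancels any constant right-left difference. Exclusion 10 and the study constraints limit heavy UV exposure and changes in hygiene or activity, sunscreen is supplied, and staff demonstrate application and repeat the demonstration. People aged 40 to 85 whose hands have stayed symmetric for decades may well not diverge much in 12 weeks. No side effect is documented, and under the planned test a 0.1 SD shift leads to rejection in only 0.4% to 7.5% of trials. This is also Version 06 of the protocol, so the 80 may already be assigned.

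Much of this stands. A large shift is not shown and may be unlikely, and a low rejection rate under the planned test is a real possibility. But these measures act on asymmetry at entry and on changes of habit. Unchanged habits can still load the two hands unequally, and a demonstration does not equalise application by side. Jar weights help little: the competitor jar could show left-hand use if it is weighed, but the HPE jar also serves the face and decolletage. Without side-reversed subjects, the comparison is valid only if δ is zero, and no data in the trial can test that.

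A further fair point is that a paired analysis on fixed sides leaves the bias unchanged and makes a side-driven result more likely to reach significance. Pairing corrects the standard error and does not cure this defect.

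**Conclusion.** The concern holds and must be fixed. As designed, a right-left difference in change cannot be credited to product rather than side, and more subjects do not help. This follows from the layout alone.

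The size of any bias is unknown. The rejection rates rest on assumed shifts and correlations and show sensitivity only. Under those assumptions, a side shift of 0.22 to 0.40 SD, depending on test and correlation, would by itself put the expected result at p = 0.05. That is of the same order as the 0.32 SD the sample could detect.

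The problem is confined to the HPE-versus-competitor aim and the hand part of the photoaging endpoint. Tolerability and facial change from baseline under HPE are not affected.

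**What to change.** 1. **Subjects not yet assigned:** randomise 1:1, in blocks, which hand receives HPE. Record side and handedness.
2. **Analysis:** use the paired within-subject difference in change from baseline, with a side term.
3. **Image reading:** before any qualitative reading, remove product and visit labels, crop to single hands and mirror-flip to a common orientation, so that side does not reveal product.
4. **Subjects already treated with fixed sides:** report the hand contrast as product plus side. Do not pool these subjects with randomised ones without a side term. Pooling 40 fixed and 40 randomised subjects (60 right, 20 left) under a 0.3 SD side shift leaves a bias of 0.3 × (60 − 20)/80 = 0.15 SD.
5. **All 80 already assigned:** only the paired analysis without a side term, the image handling and the reported limitation remain. State beside the result that pairing does not remove the side component and makes it easier for that component to reach significance.
6. **Limitation to state in any case:** the kits name both products and no subject masking is described. Randomising side does not remove differences in application by subjects who know which product is which.

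**Cost.** The change needs an amendment, a randomisation list, hand-specific labels and instructions, and perhaps a treatment-log field for the hand used. Some wrong-hand applications should be expected. It needs no extra subjects or visits and costs one degree of freedom.

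Enrolment status is unknown. If 40 or 60 of the 80 already have fixed sides and the rest are randomised 1:1, the effective n is 4/(1/60 + 1/20) = 60 or 4/(1/70 + 1/10) = 35. The detectable difference is then 0.37 or 0.48 SD, assuming the same side shift early and late. Without that assumption only the 40 or 20 randomised subjects count, with detectable differences of about 0.45 or 0.66 SD.

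If all 80 are fixed, handedness asked later gives only a weak check. With an assumed 5%, 10% or 15% left-handers (4, 8 or 12 subjects) the effective n is about 15, 29 or 41, the detectable difference is 0.73, 0.53 or 0.44 SD, and the check addresses hand dominance only.

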The site(s) or area of the skin identified for skin biopsy will be cleaned with antiseptic and may be numbed by injecting a small amount of numbing medicine, through a small needle. Some people (fewer than 1 in 10,000) are allergic to the shot you will get to numb the area where the skin is taken. The biopsy procedure is conducted by taking a larger circular tool or needle (about 1/5th of an inch in diameter), inserting it into the skin and removing the core piece that fits inside the circle. There could be bleeding from the site, and this might require placement of a stitch. Heavy bleeding from a skin biopsy is rare. Other complications could include pain, and there is the possibility of the biopsy site becoming infected. Skin biopsies cause infections about 10% of the time. A small scar will form at the biopsy site. The scar is usually much smaller than the original biopsy. The procedure is conducted using sterile instruments after disinfectant or antiseptic cleaning of the skin.

N=80 - Skin swab or Tape-stripping: Method validation will be performed at baseline visit. All subjects will be evaluated by skin swab method and tape stripping method at baseline visit. All 80 subjects will receive the skin swab method and tape stripping method at week 12 visit for microbiome analysis post-HPE treatment. All subjects will be offered skin microbiome analysis unless they did not meet criteria (i.e., washed face 3-hours prior to clinical visit, which would shift the skin microbiome; or prior allergy to adhesives) or unless they decline

In this study, bacteria will be collected by either of two methods (standard swab and tape stripping method) from your skin to culture the bacteria that normally live on the skin.

Standard swab: we will gently rub a Q-tip like swab on your skin around 4-5 times to obtain the sample.

Tape-stripping: we will use 2 specialized, transparent, adhesive disks, maintained on the skin for 1 minute to obtain the samples. You will be instructed to avoid contact with water and soap at least 3 hours prior to sample collection and refrain from wearing make-up on the day of sample collection.

Video Interview

Participants will also be asked if they would like to be part of a video interview to talk about their experience in the study and with the products.

Screening Visit / Baseline Visit (Visit 0)

The screening visit will take place prior to enrollment to determine if the potential subject is eligible to participate in the study.

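### The promised baseline validation of swab against tape has no agreement analysis or acceptance limit, and the plan's only rule for continuous data cannot show agreement

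*Combined protocol and SAP*

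**What the plan says.** The skin microbiome is a secondary endpoint (Endpoints, Secondary, item 1a). In Study procedures, the paragraph on swab and tape-stripping states: "Method validation will be performed at baseline visit". The next sentence gives the design: "All subjects will be evaluated by skin swab method and tape stripping method at baseline visit". The list at the start of that section has the same count for the baseline sample: "Left and right malar cheek untreated (n=80 with both skin swab and tape-stripping method". Both methods are scheduled again at week 12. Nothing says which microbiome summary is to be validated, by what statistic, or what result would count as success.

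The Data Analysis Plan has one rule for continuous data: "All continuous data will be analyzed using independent 2-group t tests". The fallback is also unpaired: "Nonparametric equivalents Wilcoxon rank-sum and Fisher exact tests will be used as needed for nonnormal distributions". Results are judged "with a significance level of p < 0.05". The contrasts it names are these: "Treatment effects on outcomes will be compared between baseline versus HPE and HPE versus market competitor group". Swab against tape is not among them, and no paired or agreement method appears anywhere in the plan.

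**The concern.** The design yields pairs: one swab result and one tape result per person, from the same cheeks at the same visit. Validating one sampling method against another normally asks whether the two give the same reading in the same person, or at least track each other apart from a fixed offset. The protocol does not define its question, so this is my reading of the word validation.

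A test of two independent groups answers neither question. It would give the same p-value if the tape results were shuffled among subjects, so it holds no information on within-person agreement. A non-significant result does not show that the methods agree, and a significant one does not show that they fail to track each other.

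The study will hold two sets of baseline-to-week-12 microbiome changes, one per method, with no rule on which leads. A claim that the methods are interchangeable, or a later choice to lead with one or pool both, would have no planned evidence behind it.

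**Working it through.** The documents give no power, sample-size or agreement figure for the validation, so there is nothing to reproduce. The check asks what the default test would show.

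**Inputs from the documents.** 80 subjects with both methods (an upper limit, since subjects may decline or be ineligible for sampling); independent t test or rank-sum; significance level 0.05, taken as two-sided.

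**Assumptions.** One continuous summary with SD 1 for each method, within-person correlation ρ and mean shift d in SD units. The documents give no value for ρ, d or the SD, so a range is shown.

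**Step 1: unrelated methods (ρ = 0).** With equal means, P(p ≥ 0.05) = 1 − 0.05 = 0.95. With shift d, the test statistic is centred at d√(n/2) = d√40, so P(p ≥ 0.05) ≈ Φ(1.96 − d√40).

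| Shift d | d√40 | Formula | Simulated, 40,000 runs |
|---|---|---|---|
| 0 | 0 | 95% | 94.9% |
| 0.2 | 1.26 | 76% | 76% |
| 0.3 | 1.90 | 52% | 53% |
| 0.5 | 3.16 | 11% | 12% |
| 1.0 | 6.32 | about 0% | about 0% |

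The equal-means figure hardly depends on the number sampled (94.9% at 60, 95.0% at 40), on an SD ratio of 2 (94.8%), or on using the rank-sum test (95.3%).

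**Step 2: related methods.** With equal means the true variance of the mean difference is 2(1 − ρ)/n, but the unpaired test assumes 2/n. Non-significance therefore becomes more frequent: 98.1% at ρ = 0.3, 99.4% at 0.5 and about 100% at 0.8 or more. With ρ = 0.95 and a constant offset of 0.5 SD it is about 0%. Closely tracking methods can thus do worse than unrelated ones.

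**Step 3: several measures.** If each of k independent clades had to be non-significant (equal means, unrelated methods), the chance is 0.95^k: 77% for k = 5, 60% for 10, 36% for 20.

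**Step 4: would a paired t test be enough?** No. With equal means it is non-significant in about 95% of runs whatever ρ is, and at ρ = 0.95 even a 0.2-SD offset makes it significant in almost every run. It too tests only the mean difference.

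**Step 5: an agreement analysis of the same 80 pairs.** With equal means, the 95% limits of agreement are ±1.96√(2(1 − ρ)). Lin's concordance coefficient is given as the range holding 95% of simulated values.

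| ρ | Limits of agreement | Lin's concordance |
|---|---|---|
| 0 | ±2.8 SD | −0.21 to 0.21 |
| 0.8 | ±1.24 SD | 0.70 to 0.86 |
| 0.9 | ±0.87 SD | 0.85 to 0.93 |
| 0.95 | ±0.62 SD | 0.92 to 0.97 |

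The 95% CI half-width of each limit is about 1.96√(1/80 + 1.96²/(2 × 79)) = 0.38 SD of the paired differences. So 80 pairs are enough to tell the cases apart.

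**Step 6: no single coefficient is enough.** Lin's coefficient also penalises a constant offset. With equal SDs it is 2ρ/(2 + d²). At ρ = 0.95 and d = 0.5 this is 1.90/2.25 = 0.84, while the correlation stays at 0.95 and the limits of agreement are 0.5 ± 0.62, or −0.12 to 1.12 SD. Offset, tracking and absolute agreement have to be reported separately.

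**The case against.** The best defence is that the documents assign no test to the validation. The named contrasts concern treatment effects, swab and tape are collection techniques and not groups, and the aim of the validation is undefined; it could be feasibility or yield. On that view the plan is silent here, not wrong. This largely stands: placing the swab-tape comparison under the t-test rule rests only on the rule's reach to all continuous data. But the gap remains on either reading. The comparison has an unsuitable test or none, and the remedy is the same.

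A reader might go further and infer that the plan would declare unrelated methods validated 95% of the time. The documents do not support that. Nowhere is p ≥ 0.05 defined as validation, and the 95% is simply one minus the significance level, which needs equal true means and a single measure. Steps 1 and 3 show how quickly it falls otherwise.

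It is also fair to say that little hangs on the result. Validation is not among the stated aims, the microbiome is a secondary endpoint, both methods are taken at week 12 whatever baseline shows, and the plan does not pool them or substitute one for the other. This stands and limits the priority. It does not supply the validation that the protocol promises.

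**Conclusion.** The point holds in a limited form. The protocol promises a validation on paired samples and gives no agreement analysis or acceptance limit. Its only continuous-data rule, if applied, discards the pairing and cannot show agreement. That part needs no assumed numbers.

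The size is conditional. The pass rates, from about 95% down to about 0% for unrelated methods, apply only if non-significance were read as validation, and they rest on assumed shifts, correlations and SDs. They show that the test's outcome follows the mean shift and not agreement; they do not forecast what this study would find. Tolerability and photoaging conclusions are unaffected. This is a modest but worthwhile correction to a secondary component.

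**What to change.** In the Data Analysis Plan, exempt the swab-tape comparison from the two-group tests and state that:

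- It is analysed as within-subject pairs, with the number of complete pairs reported.
- The microbiome summaries are named in advance, for example a diversity index, total yield and log-ratio abundances of the main clades.
- Each summary is reported with the mean paired difference (the offset) and 95% limits of agreement; a within-subject correlation or consistency ICC (tracking apart from offset); and Lin's concordance with its 95% CI (absolute agreement).
- The acceptance limit, and the statistic it applies to, are fixed before the data are seen. Absolute agreement is the relevant one if results might be pooled or substituted; consistency is the relevant one if a fixed offset is tolerable.
- A non-significant difference test is not evidence of validation.
- If the limit is not met, the week-12 change is reported separately by method and the methods are not called interchangeable.

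The cost is a short paragraph and a little extra analysis. Both samples are already planned at the same visit, so no subjects, visits or procedures are added. The downside is that the validation claim may come out weaker than a non-significant p-value would suggest.
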